10.4. Efficacy Analysis

In general, all patients who were treated with at least one complete cycle of study drug and have available response assessment data will constitute the efficacy population and be included in the analysis of efficacy.

The objective response rate (ORR) and duration of response, will be tabulated and summarized by descriptive statistics for patients in each indication. Progression-free survival (PFS) and overall survival (OS) will be summarized, either by tabulation, or, if feasible, by Kaplan-Meier methodology. Other efficacy analysis may be performed as appropriate.

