3. INVESTIGATIONAL PLAN

3.1. Overall Study Design and Plan

IMMU-132-01 is a Phase I/II, open-label, basket design study of IMMU-132 in adult patients with epithelial cancers expressing Trop-2. The allowed cancer types include ovarian, endometrial, cervical, breast (Triple-Negative Breast Cancer [TNBC] and non-TNBC), prostate (hormone refractory), lung (non-small cell and small-cell lung [NSCLC and SCLC], head and neck (squamous cell), esophageal, gastric, hepatocellular, renal (clear cell), thyroid, glioblastoma multiforme, colorectal, pancreatic, and urothelial cancers (UC). Eligible patients were required to have metastatic (Stage IV) disease at the time of study entry (except for glioblastoma multiforme) and be refractory to or have relapsed after at least 1 prior standard therapeutic regimen for their disease. All patients received IMMU-132 administered IV as a single agent in 3-week treatment cycles (Days 1 and 8 of 21-day cycles). Patients were to continue treatment until disease progression requiring discontinuation of treatment or unacceptable toxicity. A protocol-defined dose reduction scheme was in place to manage patients with selected AEs.

The primary objective of Phase I is to evaluate the safety and tolerability of IMMU-132 in patients with advanced epithelial cancers, using a dose escalation design to determine the maximum acceptable dose. The secondary objective of Phase I is to evaluate the PK, immunogenicity, and preliminary efficacy of IMMU-132. The primary objective of Phase II is the evaluation of the safety and efficacy of IMMU-132 at a dose selected in Phase I, while the secondary objectives of Phase II also include evaluation of PK and immunogenicity.

Screening/baseline procedures include patient history, physical examination with vital signs and performance status evaluation, local histology/pathology review to confirm 1 of the epithelial cancers listed above, safety laboratory assessments, and electrocardiogram (ECG). Tumor imaging was performed using contrast enhanced computed tomography (CT) or magnetic resonance imaging (MRI). Baseline imaging was obtained within 4 weeks of study entry. Blood/samples were collected to test for human anti-human antibody (HAHA), and uridine diphosphate glucuronosyltransferase 1A1 (UGT1A1) genotype CCI

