3.3. Phase II

In Phase II, after initially enrolled patients were evaluated in each cancer indication selected by the Sponsor in up to 2 dose levels to provide additional safety and efficacy data, indications showing a promising tumor response were considered adequate evidence of activity for further clinical development, which included TNBC, NSCLC, SCLC and UC. After initial review of patients treated at both IMMU-132 doses of 8 and 10 mg/kg, 10 mg/kg was selected for further clinical development. This dose has been received by the majority of patients in this study, including the majority of patients with mTNBC.

CCI

The enrollment of patients of the target mTNBC population was stopped on 14 February 2017 since the enrollment goals were met after a total of 148 mTNBC patients had been entered, but the enrollment of patients in other cancer indications continued. Subsequently, in June 2017, the Sponsor notified the sites of the decision to stop further enrollment of patients into the study, and the last patient enrolled occurred on 22 June 2017.

CCI

CCI

CCI

CCI

CCI

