4. ANALYSIS POPULATIONS

Given that this study was conducted as a Phase I/Phase II and included a diverse population comprised of patients with different tumor types, it is necessary to define specific patient populations. The following sections outline the populations to be included for the evaluation of efficacy and safety. The patient populations to be used are:

- Target mTNBC Population: Patients with relapsed/refractory mTNBC who have received at least 2 prior therapies for metastatic disease and who received IMMU-132 at a dose of 10 mg/kg.
- Per-Protocol (PP) Population (specific to the Target mTNBC Population): This will include patients of the Target mTNBC Population who received at least 1 complete cycle of IMMU-132 and had data available from at least 1 response assessment.
- Overall Safety Population: This will include all patients who received at least 1 dose of IMMU-132, irrespective of dose, tumor type, or number of prior therapies.

At the time of final SAP (version 3.0), the following patient populations are added for safety and efficacy analyses:

- Metastatic, non-triple-negative breast cancer (mBC) Population: This will include all patients with hormone receptor-positive/human epidermal growth factor receptor 2-negative (HR+/HER2-) metastatic breast cancer (mBC) who progressed on at least 1 prior hormonal therapy in the metastatic setting and who received at least 1 dose of IMMU-132 at a dose of 10 mg/kg.
- Metastatic Urothelial cancer including urinary bladder (mUC) Population: This will include all mUC patients who had relapsed after or were refractory to at least 1 prior standard therapeutic regimen and who received at least 1 dose of IMMU-132 at a dose of 10 mg/kg.

And the following patient populations are added for limited efficacy analyses:

- Small-cell lung cancer (SCLC) Population: This will include all SCLC patients as enrolled in the study in accordance with the eligibility criteria and who received at least 1 dose of IMMU-132.
- Non-small-cell lung cancer (NSCLC) Population: This will include all NSCLC patients as enrolled in the study in accordance with the eligibility criteria and who received at least 1 dose of IMMU-132.
- Colorectal (CRC) Population: This will include all CRC patients as enrolled in the study in accordance with the eligibility criteria and who received at least 1 dose of IMMU-132.

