- Esophageal cancer (EGC) Population: This will include all EGC patients as enrolled in the study in accordance with the eligibility criteria and who received at least 1 dose of IMMU-132.
- Endometrial cancer (EMC) Population: This will include all EMC patients as enrolled in the study in accordance with the eligibility criteria and who received at least 1 dose of IMMU-132.

- Pancreatic ductal adenocarcinoma (PDC) Population: This will include all PDC patients as enrolled in the study in accordance with the eligibility criteria and who received at least 1 dose of IMMU-132.

For the mTNBC target population of 108 patients, it was ensured that all patients had a minimum of 4 months follow-up. This allowed to include at least 2 post-baseline assessments (except for patients who died or discontinued study treatment prior to their second post-baseline scan).

CCI

At the time of final analyses, because of the additional enrollment up until 22 June 2017, the Overall Safety Population increased to approximately 495.

CCI

Subsequently, for the final data analyses to support CSR, the targeted data cut-off date is planned on 01 March 2019. If different, the actual data cut-off will be stated in the CSR. The cut-off date applies to both the Overall Safety Population and individual cancer populations.

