5. STATISTICAL ANALYSES

Throughout this SAP, efficacy data will be summarized for the Target mTNBC Population, mBC, mUC, SCLC, NSCLC, CRC, EGC, EMC and PDC Population, with all patients in the respective population combined, while safety data will be summarized for the Target mTNBC Population, mBC Population, mUC Population and the Overall Safety Population. For the Overall Safety Population, data will be summarized by dose group (defined as assigned dose) and overall.

All data will be listed for the Overall Safety Population and where applicable, in the cancer-specific analysis population, as specified.

Screen failures and entered-but-not-dosed patients will be excluded from all analyses.

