9. INTERIM ANALYSIS

Analyses based on data from the 30 June 2017 cut-off conducted under SAP version 2.0 CCI

Various administrative interim analyses had been conducted to support clinical development decisions or public data disclosures or publications. The final analyses are conducted under SAP version 3.0 based on the planned data cut-off date of 01 March 2019.

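### Protocol 10.4 promises response summaries for each indication, but the visible SAP gives them for nine populations, eight added after enrolment ended; nine allowed tumour types and parts of three others have none

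*Protocol*

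**What the plan says.** **Protocol.** Section 10.4 says that ORR and duration of response "will be tabulated and summarized by descriptive statistics for patients in each indication". Its efficacy population is "all patients who were treated with at least one complete cycle of study drug and have available response assessment data", with no limit by tumour type, dose or prior lines. Section 2.1 makes efficacy part of the Phase II primary objective. The synopsis allows up to 150 assessable patients in each of five subtypes and up to 56 in each other cancer type.

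**SAP scope.** Section 3.1 gives the eligible tumours in a list that starts "The allowed cancer types include ovarian, endometrial, cervical, breast (Triple-Negative Breast Cancer [TNBC] and non-TNBC), prostate (hormone refractory), lung" and runs to 18 types. Section 5 then states that "efficacy data will be summarized for the Target mTNBC Population, mBC, mUC, SCLC, NSCLC, CRC, EGC, EMC and PDC Population". Tables 1 and 2 in Section 4.4 leave the efficacy row blank for the Overall Safety Population. Section 4.1 offers data listings on that population.

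**SAP population definitions (Section 4).** Target mTNBC requires at least two prior therapies for metastatic disease and 10 mg/kg. Section 3.3 says that "the enrollment goals were met after a total of 148 mTNBC patients had been entered", whereas Section 4 speaks of its minimum follow-up "For the mTNBC target population of 108 patients". The mBC population is restricted to HR+/HER2- disease that progressed on hormonal therapy, at 10 mg/kg. The mUC population is restricted to 10 mg/kg. The other six populations take any dose.

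**SAP timing.** Section 4 marks mBC and mUC as added at version 3.0 and continues "And the following patient populations are added for limited efficacy analyses", listing six more. Section 9 refers to the 30 June 2017 cut-off and says that "Various administrative interim analyses had been conducted to support clinical development decisions".

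**The concern.** In a basket trial, a response rate in one tumour type is read against the rates in the others. A reader needs a denominator and a rate for every type treated, including those with little or no activity. The Protocol promises this; the visible SAP gives it for half of the allowed types. Most of the set was fixed in an open-label study after enrolment had closed and after analyses had been used for development decisions, disclosures or publications. The readable text gives no reason why these types were chosen and the others left out. With no hypothesis tests planned, the risk is not an inflated error rate. It is a selective display of descriptive results on a primary objective.

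A second gap lies inside indications that do have a population. Target mTNBC, mBC and mUC are narrower than the tumour types they represent, so an indication means different things in different rows of the same report.

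**Working it through.** The documents state no derived figure on this point, so the check compares lists, counts and dates.

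**1. Tumour types without an efficacy population**
- Allowed types, SAP 3.1, counting TNBC and non-TNBC, and NSCLC and SCLC, separately: 18.
- Efficacy populations, SAP 5: Target mTNBC, mBC, mUC, SCLC, NSCLC, CRC, EGC, EMC, PDC = 9.
- 18 - 9 = 9 without one: ovarian, cervical, prostate, head and neck, gastric, hepatocellular, renal, thyroid, glioblastoma.
- Cross-check: Protocol Section 3 lists 16 types, omitting colorectal and pancreatic. Seven of its 16 have a population, and 16 - 7 = 9, the same nine types.
- Enrolment in these nine is not given. Protocol Section 1 mentions one gastric patient among those added at 8 mg/kg.

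**2. mTNBC patients outside the target population**
- 148 entered (SAP 3.3) - 108 in the target population (SAP 4) = 40; 40/148 = 27.0%.
- This is an upper limit. The 148 are entered, not stated as dosed, and SAP 5 excludes undosed patients from all analyses. Protocol 10.4 also requires one complete cycle and response data.

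**3. How far an all-mTNBC rate could differ.** Assume all 40 were treated. If x of the 108 respond, the pooled rate lies between x/148 and (x + 40)/148. The values of x are assumptions, because the documents give no response count.

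| Assumed responders in 108 | Lower bound | Upper bound |
|---|---|---|
| 22 (20%) | 22/148 = 14.9% | 62/148 = 41.9% |
| 32 (30%) | 32/148 = 21.6% | 72/148 = 48.6% |
| 43 (40%) | 43/148 = 29.1% | 83/148 = 56.1% |

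These are arithmetic extremes. In the 30% row, if the 40 respond at half to one and a half times that rate (6 to 18 responders), the pooled rate runs from 38/148 = 25.7% to 50/148 = 33.8%.

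**4. Timing**
- Last patient enrolled 22 June 2017 (SAP 3.3); data cut-off 30 June 2017 (SAP 9); SAP v3.0 dated 01Feb2019. From June 2017 to February 2019 is about 19 months.
- Populations marked as added at v3.0: 2 (mBC, mUC) + 6 (SCLC, NSCLC, CRC, EGC, EMC, PDC) = 8.
- The SAP version history shows v2.0 (14Mar2018) revising the size of the Target mTNBC Population, so that population already existed. When it was first defined cannot be read from the text.

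**5. Overlap with reported responses.** The Protocol synopsis and Section 1 name six types with partial responses: TNBC, SCLC, NSCLC, esophageal, urinary bladder and colorectal. All six have a population, and none of the nine omitted types is named. Three covered groups (non-TNBC breast, endometrial, pancreatic) are not named either.

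**The case against.** The strongest reply is that version 3.0 widened reporting, from one cancer-specific efficacy population to nine, and so moved the SAP closer to Protocol 10.4. That is correct. The criticism is that the widening stopped short of the commitment, not that it narrowed anything.

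A reader might infer from the dates and the overlap in step 5 that cohorts were picked because they responded. The documents do not support this. Three included groups are not on the reported-response list, no outcome is given for any omitted type, and Section 9 does not say which tumour types the administrative analyses covered. Nor is there support for describing the nine omitted types as failures.

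Redaction is a fair caution. Parts of SAP 4.1 and 6.9 are hidden, the subgroup section 6.10 is not readable, and Section 11, where changes from the Protocol belong, is blacked out. A justification may sit there. However, Section 5 and Tables 1 and 2 are readable and set the scope of the efficacy summaries.

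The SAP was written against the Protocol of 24 April 2017 (through Amendment 11), while the text quoted here is the January 2020 revision. The mismatch is therefore between the current versions of the two documents. The later revision kept the commitment about a year after SAP v3.0. The Protocol does not define what counts as an indication.

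Two further replies carry less weight. Listings cover all treated patients but give no denominator, rate or interval. The absence of hypothesis tests does not make a selective display harmless.

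**Conclusion.** The inconsistency stands. Protocol 10.4 commits to ORR and duration of response for each indication, and the visible SAP provides them for nine populations, eight of them added after enrolment and after looks at the data. Nine of 18 allowed tumour types have no visible response summary. Neither do up to 40 of the 148 mTNBC patients entered, nor an unstated number of non-TNBC patients outside the mBC definition and of urothelial patients not treated at 10 mg/kg.

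Two stronger statements should be avoided: that all nine populations were chosen late, since Target mTNBC predates v2.0; and that 40 treated mTNBC patients were left out, since 40 is only a ceiling.

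The conclusion rests on the readable text and on taking an indication to mean a tumour type on the eligibility list. The number of patients affected outside mTNBC is unknown, and a type that enrolled nobody needs no summary. The plan is exposed to selective reporting; selective reporting itself is not shown. The sponsor should correct this, and the correction is a cheap improvement.

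**What to change.** Add one descriptive table to SAP Section 6, with a row for every indication that enrolled at least one treated patient. Give the number with confirmed CR or PR, the denominator and the exact 95% CI already specified in SAP 6.2, by starting dose. Show it for all treated patients and for the Protocol 10.4 efficacy population, with duration of response for responders. Include rows for all treated mTNBC, all treated non-TNBC and all treated urothelial patients. Keep the nine populations for the fuller analyses. If Section 11 does not already do so, state there why those populations were chosen.

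The cost is one extra table from data already collected. SAP 7.1 already groups adverse events by type of malignancy in the Overall Safety Population, so the same grouping can be used. The downside is imprecision in small cohorts. With no responders among n patients the exact upper limit is 1 - 0.025^(1/n), which is 97.5% for n = 1 and 6.4% at the Protocol's ceiling of n = 56. The interval shows that imprecision plainly.

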10.5. Other Evaluations

Because of the escalation design, the dose levels and the number of patients entered on each dose level in this study cannot be determined in advance. Pre - and post-dose serum samples for peak and trough drug concentrations will be collected in all patients. Once the MTD level is known, additional patients accrued to that level will have additional serum taken to better define the rate of clearance after each injection. This will provide adequate data to allow for the determination of potential drug accumulation with repeated dosing. Antibody pharmacokinetics will be evaluated in a separate report based on blood levels of IMMU-132 from a subgroup of patients as measured by the

Sponsor in order to characterize concentration levels during treatment (See Study Calendar for time points).

Descriptive statistics will be used to summarize both peak and trough values at each infusion as well as values measured at other time-points. Formal pharmacokinetic analysis based on a non-compartmental model will be performed on patients with adequate serum concentration data, if feasible. Additional analyses may also be performed to evaluate serum levels of SN-38, if feasible, and to study the correlations between IMMU-132 concentrations and various treatment outcomes.

10.6. Interim Analysis

No formal interim analysis is planned during the course of this study.

11. TREATMENT COMPLIANCE

IMMU-132 will be administered at scheduled study centers under the supervision of the Investigator or sub-investigator(s). The pharmacist will maintain records of study drug receipt, preparation, and dispensing, including the applicable lot numbers, patient's height, weight and total drug administered in milligrams. Any discrepancy between the calculated dose and dose administered and the reason for the discrepancy must be recorded in the source documents and on appropriate CRF.

12. QUALITY CONTROL AND QUALITY ASSURANCE

The Sponsor has ethical, legal and scientific obligations to follow this study carefully in a detailed and orderly manner in accordance with established research principles and applicable regulations. Monitoring visits to the study site will be conducted periodically during the study to ensure that good clinical practice (GCP) and all aspects of the protocol are followed. The trial site may also be subject to review by the IRB/IEC, to quality assurance audits performed by Immunomedics, and/or to inspection by appropriate regulatory authorities. Investigator(s) and their relevant personnel must agree to be available and participate with visits conducted at a reasonable time in a reasonable manner, and the Investigator/Institution must guarantee direct access to source documents by Immunomedics and its designee, and appropriate regulatory authorities.

Regulatory authorities worldwide may also audit the Investigator during or after the study. The Investigator should contact the Sponsor immediately if this occurs and must fully cooperate with regulatory authority audits conducted at a reasonable time in a reasonable manner.

13. DATA HANDLING AND RECORD KEEPING

13.1. Case Report Forms

A CRF is required and must be completed for each enrolled patient. The completed original CRFs are the sole property of Immunomedics and should not be made available in any form to third parties, except for authorized representatives of appropriate regulatory authorities, without written permission from Immunomedics.

It is the Investigator's responsibility to ensure completion and to review and approve all CRFs. CRFs must be signed by the Investigator or by an authorized staff member. These signatures serve to attest that the information contained on the CRFs is true.

At all times, the Investigator has final personal responsibility for the accuracy and authenticity of all clinical and laboratory data entered on the CRFs. Patient source documents are the physician's patient records maintained at the study site. In most cases, the source documents will be the hospital's or the physician's chart. In cases where the source documents are the hospital or the physician's chart, the information collected on the CRFs must match those charts. In some cases, a portion of the source documents for a given study site may be the CRFs. The Investigator must agree which items will be recorded in the source documents and for which items the CRF will stand as the source document.

All entries in the CRF should be made legibly with black ballpoint pen. Corrections to the CRF must be made by striking through the incorrect entry with a single line and entering the correct information adjacent to the incorrect data. The correction must be initialed and dated by the person making the correction (ICH E6 4.9.3).

13.2. Record Retention

To enable evaluations and/or audits from regulatory authorities or Immunomedics, the Investigator agrees to keep records, including the identity of all participating patients (sufficient information to link records, CRFs and hospital records), all original signed informed consent forms, copies of all CRFs, source documents, and detailed records of treatment disposition. The records must be retained by the Investigator until 2 years after the last approval of a marketing application in an ICH region and until there are no pending or contemplated marketing applications in an ICH region, or until at least 2 years have elapsed since the formal discontinuation of clinical development of the investigational product. However, study records may be retained for a longer period if required by local regulations. The Sponsor is responsible for informing the Investigators when these documents need no longer be retained.

If the Investigator relocates, retires, or for any reason withdraws from the study, Immunomedics should be prospectively notified. The study records must be transferred to an acceptable designee, such as another Investigator, another institution, or to Immunomedics. The Investigator must obtain Immunomedics written permission before disposing of any records.

